15.1.1.1. NATIONAL CANCER INSTITUTE COMMON TERMINOLOGY CRITERIA FOR ADVERSE EVENTS (CTCAE) GRADE

Severity is based on NCI CTCAE v.4.03 grades and classed as mild, moderate, severe, life threatening, or death related to AE (increasing severity), as represented by Grades 1-5, respectively. TEAEs starting after the first dose of study drug with a missing severity will be classified as ‘missing’. If a patient reports the same AE more than once within that SOC/PT, the AE with the worst-case severity will be used in the corresponding severity summaries. In determining maximum severity, response values will be ranked in order from minimum severity to maximum severity as Missing, Grade 1, Grade 2, Grade 3, Grade 4, and Grade 5 (as values: ‘missing’, ‘mild’, ‘moderate’, ‘severe’, ‘life threatening’, and ‘death related to AE’).

A summary table will present TEAEs, showing number of subjects (%) for all grades and grades ≥ 3 for each SOC/PT. This summary table will also be repeated for TEAEs related to IMCgp100.

15.1.1.2. RELATIONSHIP TO STUDY DRUG (IMCGP100)

Relationship, as indicated by the investigator, is classed as unrelated or related. The categories ‘possibly’ related or ‘related’ will be pooled to create the ‘related’ category. TEAEs with a missing relationship to study drug will be regarded as ‘missing’.

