## 8.3 Assessment of Causality

### 8.3.1 Causality Assessment Required for All Adverse Events

The investigator decides whether he or she interprets the observed AE as either related to disease, to the study medication, study procedure, or other concomitant treatment or pathologies. To assess the relationship of the AE to the study drug, the following terms are defined:

- (1) Related: A direct cause and effect relationship between the study treatment and the AE is likely
- (2) Possibly related: A cause and effect relationship between the study treatment and the AE has not been demonstrated at this time and is not probable, but is also not impossible
- (3) Unrelated: Without question, the AE is definitely not associated with the study treatment

All “related” and “possibly related” AEs and SAEs will be defined as related to study drug.

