15.1. Adverse Events

Patients with multiple adverse events in the same category are counted only once in that category and those with adverse events in more than 1 category are counted once in each of those categories. Adverse Events (AEs) will be coded using Medical Dictionary for Regulatory Activities (MedDRA) central coding dictionary, using the latest version of MedDRA available at the time of coding for the reporting period.

Treatment-emergent adverse events (TEAEs) are defined as AEs that started or worsened in severity from the date of first dose of the rollover study (regardless of time) up until 90 days after the last dose of study drug of this rollover study.

See [APPENDIX 2](#) for handling of partial dates for AEs. In the case where it is not possible to define an AE as treatment-emergent or not, the AE will be classified by the worst case; i.e. treatment emergent.

An overall summary of number of patients within each of the categories described in the subsection below, will be provided as specified in the templates.

An AE Listing will include TEAEs and Non-TEAEs, including those from before the first dose in the parent study and post-treatment periods which will be flagged as such. Only TEAEs will be summarized.

AE Structure as Recorded in the eCRF:

AEs will be recorded in the eCRF such that any change in severity over the course of their duration will be recorded as a single record. The AE/SAE eCRF page collects ‘Initial Grade’ and ‘Most Extreme Grade’ but not the date of the severity grade change. No further manipulation post collection is required, and the AE/SAE data will be listed as recorded.

The definition of a treatment-emergent AE will be handled for AEs that change in severity over the course of their duration, by assuming that any AE that *might have worsened* in severity within the timeframe from the date of first dose of the rollover study (regardless of time) up until 90 days after the last dose of study drug, will be defined as treatment-emergent. A worsening severity is defined as changing from a less severe (lower) CTCAE grade to a more severe (higher) CTCAE grade. For example, if an AE started prior to date of first dose of the parent study but ended on or after date of first dose of the parent study (regardless of time), and the ‘Most Extreme Grade’ is more severe (higher) than the ‘Initial Grade’, then the AE is assumed to be treatment-emergent.

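### TEAEs with missing causality stay out of the related-TEAE table, so the related count is a lower bound whenever any causality is missing

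*SAP*

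**What the plan says.** SAP 15.1.1.2 takes the investigator's causality judgement and reduces it to two classes: the possibly related and related categories "will be pooled to create the" related class. It then adds that "TEAEs with a missing relationship to study drug will be regarded as" missing. SAP 15.1.1.1 repeats the system organ class and preferred term table, with its all-grades and Grade 3 or higher columns, for TEAEs related to IMCgp100. An event in the missing class does not qualify for that repeat.

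Protocol 8.3.1, headed "Causality Assessment Required for All Adverse Events", defines three judgements. The third is "Unrelated: Without question, the AE is definitely not associated with the study treatment". The other two are merged: related and possibly related "AEs and SAEs will be defined as related to study drug". The section has no rule for an event without an assessment.

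For an AE whose treatment-emergent status cannot be determined, SAP 15.1 says that "the AE will be classified by the worst case", which means treatment-emergent. SAP 7.3 says in general that missing data are not imputed.

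**The concern.** The primary objective (Protocol 4.1, SAP 2.1) and the endpoint in Protocol 4.3 are worded as AEs associated with IMCgp100. The table that carries attribution is the related-TEAE repeat. An event that nobody has assessed has the same numerical effect there as one judged unrelated: neither is counted. Yet the protocol sets a high bar for calling an event unrelated, and an unassessed event has not met it.

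The handling is also uneven. An AE of unknown timing is brought into the TEAE tables by assuming the worst case; the same AE with unknown causality is then left out of the related table. At stake is whether a reader takes the related count as the full count when it is only its lower limit, with nothing in the described outputs to show how far the upper limit lies above it.

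**Working it through.** The plan states no sample size (Protocol 9.9), no expected AE rate and no missing-causality rate, so there is no figure of its own to reproduce. The check has three steps.

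**1. Direction.** For any table row, let R be the number of patients with at least one TEAE recorded as related or possibly related. Let M be the number with no such event but at least one TEAE of missing causality. Patients are counted once per category (SAP 15.1), so:

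- count under SAP 15.1.1.2: R
- count with missing treated as related: R + M
- count T that full assessment would have given: R ≤ T ≤ R + M

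The SAP count can never exceed T. It falls below T only if a patient's sole related events in that row are among those with missing causality. If M = 0, the three counts agree.

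**2. Size per affected patient.** One patient in M is worth 1/N. With N assumed:

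- N = 10: 1/10 = 10 percentage points
- N = 20: 1/20 = 5 points
- N = 30: 1/30 = 3.3 points

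**3. Illustration of both bounds.** Assume m TEAEs per patient in the row, probability p that a TEAE is related, and a share q with causality missing completely at random, all independent. The probability that a patient is counted is:

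- full assessment: 1 − (1 − p)^m
- SAP rule: 1 − (1 − p(1 − q))^m
- missing counted as related: 1 − ((1 − p)(1 − q))^m

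| m | p | q | Full assessment | SAP rule | Missing as related |
|---|---|---|---|---|---|
| 1 | 0.5 | 5% | 50.0% | 47.5% | 52.5% |
| 5 | 0.5 | 5% | 96.9% | 96.0% | 97.6% |
| 10 | 0.5 | 5% | 99.90% | 99.84% | 99.94% |
| 1 | 0.8 | 10% | 80.0% | 72.0% | 82.0% |
| 2 | 0.3 | 10% | 51.0% | 46.7% | 60.3% |

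Over m = 1, 2, 5, 10, p = 0.3, 0.5, 0.8 and q = 1%, 5%, 10%, the shortfall under the SAP rule runs from about 0 to 8.0 points (80.0 − 72.0). The overstatement when missing is counted as related runs from about 0 to 9.3 points (60.3 − 51.0). With one event per patient the two errors are pq and (1 − p)q, so which bound lies nearer the truth depends on p. Both errors are largest with one or two events per patient in the row. With many events per patient they shrink: at m = 10 neither exceeds 1.9 points anywhere in the grid, and at p = 0.5 or more both are below 0.2 points.

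**The case against.** The strongest reply is that SAP 15.1.1.2 follows the SAP's own general rule. SAP 7.3 says no imputation, and a separate missing class is what that rule implies. A reader might infer that the SAP breaks a worst-case principle of its own. The documents do not support that: the worst-case wording covers timing only, namely treatment emergence (SAP 15.1) and the prior, concomitant or post status of medications (SAP 12). What stands is a difference in approach between fields. SAP 7.3 is not absolute either, since Appendix 2 and SAP 10.1 impute partial dates.

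A reader might also infer that the SAP calls unassessed events unrelated. It does not; it holds them apart, and Protocol 8.3.1 is silent on missing values. The bar set there for an unrelated judgement is a reason to prefer the conservative direction, not a rule that the SAP breaches.

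Nor do the documents support saying that the primary safety figure is biased low. Table 4-1 and Protocol 9.5.1 give the incidence of AEs without a causality restriction, and the all-TEAE table of SAP 15.1.1 includes every event whatever its causality.

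Missing values should also be few. Causality is required for all AEs, the proposed relationship is part of the minimum SAE information (Protocol 8.5), and missing values are queried (Protocol 10.4). Nothing in the documents shows that missing causality clusters in late or poorly followed events. These points limit the size of the effect but do not remove the lower-bound property.

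Finally, counting all missing as related can overstate, as the working shows. The table shells are not among the documents, so a missing row may already be planned.

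**Conclusion.** The point holds as a limited one. Under SAP 15.1.1.2 the related-TEAE count is a lower bound whenever causality is missing, and the SAP describes no count that shows the upper bound. This touches the primary objective as worded in Protocol 4.1 and 4.3 and SAP 2.1, but not the all-AE variable of Protocol 9.5.1.

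The effect is zero if all causality is obtained. Otherwise it is 3.3 to 10 percentage points per affected patient for an assumed 30 to 10 patients, and only for a patient with no other related event in that row. The illustrative range of 0 to 8.0 points rests on assumed event numbers, relatedness and missing rates, not on trial data.

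The ranking of missing grade is sometimes read as part of the same problem, because "response values will be ranked in order from minimum severity to maximum severity as Missing, Grade 1" and upwards. It is not: an ungraded event stays in the all-grades column and the related count does not change. The ranking can lower only the Grade 3 or higher column, and treating every ungraded event as Grade 3 or higher would be a strong assumption without support in the documents.

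**What to change.** In SAP 15.1.1.2, count TEAEs with missing relationship as related in the related-TEAE summary, and state this as an exception to SAP 7.3. Footnote the number of events so counted and the number of patients who enter only because of them; subtracting those patients recovers the lower bound, so both bounds are visible. Keep the value as missing in the listing. For missing grade, at most footnote the number of TEAEs concerned in SAP 15.1.1.1 and leave the ranking as it is.

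The cost is one rule, its stated exception and a footnote, settled before database lock so that the choice does not depend on the data. The downside is a related count that may be slightly too high. If no causality is missing, the counts do not change.

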15.1.2. TEAEs Leading to Discontinuation of Study Drug

TEAEs leading to permanent discontinuation of study drug will be identified by using the ‘Action taken with the study drug’ variable collected on the eCRF, where the variable is equal to ‘Drug permanently discontinued’. These will be flagged in the listing.

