## 6.6 Treatment Discontinuation

Reasons for discontinuation of study treatment will include:

- Unequivocal PD, see [Section 6.6.1](#)
- Loss of clinical benefit from treatment with IMCgp100 in the opinion of the principal investigator or the initiation of alternative anti-cancer therapy (including another investigational agent)
- Unacceptable toxicity defined as an AE that, in the opinion of the investigator or the Sponsor, contraindicates further dosing, including  $\geq$  grade 3 cytokine release syndrome
- Withdrawal of consent from further treatment with investigational product by the patient or the investigator or lost to follow-up
- Patient is determined to have failed to meet selection criteria for the study AND continuing to receive investigational product might constitute a safety risk. Patients who fall into this category and for whom continuation of study treatment is not thought to pose a safety risk in the opinion of the investigator may continue to receive study treatment after discussion with the Sponsor
- Pregnancy or intent to become pregnant

At the time patients discontinue study treatment, the EOT visit should be scheduled in the appropriate window of 14 days after the last dose was administered. At this visit, all of the assessments listed for the EOT visit will be performed (see [Table 7-1](#)). If the decision to withdraw the patient occurs at a regularly scheduled visit, that visit may become the EOT visit rather than having the patient return for an additional visit (EOT follow-up will still continue for the full 14-day observation period, see [Section 7.2](#) for details of assessments required). An End of Treatment eCRF page should be completed at the EOT visit, giving the date and reason for stopping the study treatment. End of treatment/premature withdrawal visit is not considered as the end of the study.

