## 8 ADVERSE EVENTS AND SAFETY REPORTING

### 8.1 Assessment of Safety

All patients who receive any treatment with IMCgp100 will be considered evaluable for safety. All AEs, regardless of study drug relationship, will be collected through the 90-day Safety Follow-up Period. At the time of consent, if any patient has any ongoing AE(s) from the parent IMCgp100 study, the AE(s) will be captured on the eCRF page and the "Ongoing at Start of Study" must be answered "Yes". The start date recorded in the eCRF for the rollover study should be equal to the start date of the event as recorded in the parent study. Timely, accurate, and complete reporting and analysis of safety information from clinical studies are crucial for the protection of patients and is mandated by regulatory agencies worldwide. The Sponsor and CRO have established standard operating procedures in conformity with regulatory requirements worldwide to ensure appropriate reporting of all safety information. All clinical studies conducted by the Sponsor or its affiliates will be conducted in accordance with those procedures.

Individual AEs should be evaluated by the investigator and should be reported to the CRO/Sponsor for evaluation. This includes the evaluation of the event's seriousness and the causality between the investigational medicinal product(s) and/or concomitant therapy and the AE. The CRO/Sponsor is required to maintain detailed records of all AEs reported by the investigator(s) and to perform an evaluation with respect to seriousness, causality, and expectedness. On request of a competent authority in whose territory the clinical trial is being conducted, the Sponsor should submit detailed records of all AEs which are reported by the relevant investigators. Case report processing concerns evaluation of data in individual cases, identification of individual cases requiring specific handling, recognition and processing of alerts, and any other data processing of aggregated cases.

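### SAP 15.1.2 looks for AE-related stops only among TEAEs, so whether a stop caused by an unworsened carried-over AE is flagged and counted depends on which of two conflicting TEAE anchor dates is applied

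*SAP*

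**What the plan says.** SAP 15.1.2 defines the discontinuation category: "TEAEs leading to permanent discontinuation of study drug will be identified by using the" action-taken variable, where the answer is permanent discontinuation. It continues: "These will be flagged in the listing".

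SAP 15.1 sets what counts as a TEAE: "AEs that started or worsened in severity from the date of first dose of the rollover study", up to 90 days after the last rollover dose. On tabulation it says "An overall summary of number of patients within each of the categories described in the subsection below, will be provided", following the templates, and adds "Only TEAEs will be summarized".

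Protocol 8.1 explains how earlier events enter the data: "if any patient has any ongoing AE(s) from the parent IMCgp100 study, the AE(s) will be captured on the eCRF page", marked as ongoing at start of study and keeping the start date recorded in the parent study.

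Protocol 6.6 lists the relevant reason for stopping without any condition on when the event began: "Unacceptable toxicity defined as an AE that, in the opinion of the investigator or the Sponsor, contraindicates further dosing".

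Appendix 2 of the SAP gives the date algorithm for treatment emergence, including the case where the start date is fully known. A note below it defines the study drug start date as the first drug date in the parent study.

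**The concern.** In a rollover study the start of an AE and the decision to stop for it can fall in different studies. A toxicity may begin in the parent study, persist at the same grade, and finally lead the investigator to stop IMCgp100 in the rollover. The stop is then an outcome of rollover treatment; only the onset is earlier. If the discontinuation category is limited to TEAEs and the TEAE clock starts at the first rollover dose, that stop is neither flagged nor counted as AE-related.

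This bears on the study's own questions. The primary objective concerns AEs associated with IMCgp100, and a secondary objective concerns safety and tolerability beyond one year of dosing. Persistent toxicity that ends treatment is part of that answer. A reader could also find a stop for toxicity in the disposition output with no flagged AE to explain it.

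**Working it through.** The plan gives no figure to reproduce: Protocol 9.9 sets no sample size and SAP 6.5 plans no hypothesis tests. The check applies each TEAE rule to the same patient.

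**Inputs from the documents**
- Selection for the flag: TEAEs with action taken 'Drug permanently discontinued' (SAP 15.1.2).
- Start date of a carried-over AE: the parent-study start date (Protocol 8.1).
- Rule A, the SAP 15.1 definition: TEAE if the AE started or worsened between the first rollover dose and last rollover dose + 90 days.
- Worsening under Rule A: the eCRF holds 'Initial Grade' and 'Most Extreme Grade' but no date of change, so an AE that might have worsened in the window counts as a TEAE.
- Rule B, Appendix 2 with known dates: TEAE if study drug start ≤ AE start ≤ study drug end + 90, where study drug start is the first parent-study dose. The worked example in SAP 15.1 uses the parent-study dose too.

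**Test case (days assumed for illustration).** First parent dose day -200; first rollover dose day 1; last rollover dose day 100. The window closes at 100 + 90 = day 190. The AE starts on day -30, is ongoing at entry, and has action 'Drug permanently discontinued'.

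| AE | Rule A (rollover anchor) | Rule B (parent anchor) |
|---|---|---|
| Start day -30, most extreme grade = initial grade | -30 < 1 and no worsening: not a TEAE, so not flagged or counted | -200 ≤ -30 ≤ 190: TEAE, so flagged and counted |
| Start day -30, most extreme grade > initial grade | Might have worsened in the window: TEAE | -200 ≤ -30 ≤ 190: TEAE |
| Start day 10 | 1 ≤ 10 ≤ 190: TEAE | -200 ≤ 10 ≤ 190: TEAE |

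Of these cases, the rules disagree only in the first row: a carried-over AE that never exceeded its initial grade and still led to a stop.

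**Size.** Each missed patient lowers the AE-discontinuation percentage by 100/N points. N is not stated, so as assumed values:
- N = 5: 100/5 = 20 points
- N = 10: 100/10 = 10 points
- N = 20: 100/20 = 5 points

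If no such stop occurs, the error is 0. It cannot be positive, because the TEAE restriction only removes records.

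**The case against.** The strongest reply is that the SAP's own algorithm already captures this patient. Appendix 2 covers fully known dates as well as partial ones, and its note fixes the anchor at the first parent-study dose. The worked example in 15.1 agrees with it. This stands: a reader might infer from 15.1 and 15.1.2 that the patient is certain to be missing, and the documents do not support that. They support a contradiction. It does not rescue the plan, because the result depends on which passage the programmer follows. If the conflict is settled in favour of the 15.1 definition, which matches the observation periods in SAP 15 and Protocol 9.6.1, the omission becomes definite.

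Second, the gap is narrow. The 'might have worsened' rule brings in any AE still present in the window whose most extreme grade exceeds its initial grade, even if it actually worsened in the parent study. Protocol 5.1 also bars entry with ongoing serious IMCgp100-related toxicity that would preclude dosing. Both points stand.

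Third, a reader might infer that the responsible event disappears from the report. It does not. The AE listing includes non-TEAEs, SAP 9 presents discontinuations for all enrolled patients, and Protocol 9.4 has the reason for stopping summarized and listed. What is lost is the flag tying the stop to its event, and the AE-based count.

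Fourth, 15.1.2 itself promises only a listing flag. A count follows from the overall summary in 15.1, whose templates are not among the documents, so the effect on a count is conditional.

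Finally, a reader might go further and fault the SAP for leaving persistent parent-study AEs out of its AE tables generally. Protocol 9.6.1.1 limits those tables to new or worsened on-treatment AEs, and the SAP follows it. A general summary row for AEs ongoing at entry would be a preference and is not requested here.

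**Conclusion.** The point holds in a limited form. For an AE that began after the first parent-study dose, stayed at its initial grade and led to stopping IMCgp100 during the rollover, the SAP gives opposite answers: outside the discontinuation flag and count under the 15.1 definition, inside them under Appendix 2. The exposure is confined to the AE-based flag and to any count of that category in the overall AE summary. Any error runs low, by 100/N percentage points per missed patient. The documents give neither N nor an expected number of such stops, so a definite bias cannot be claimed.

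The restriction is also out of step with its neighbours. SAP 15.1.3 lists SAEs by the seriousness answer, and 15.1.4 lists any AE leading to death, neither with a treatment-emergence condition on the listing. The change is worth making because the output concerns long-term tolerability and the data needed are already collected.

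**What to change.** 1. In SAP 15.1.2, define the category as any AE record whose action taken is 'Drug permanently discontinued' during the rollover, whatever its treatment-emergent status. Flag and count these records, split into TEAEs and non-TEAEs marked 'Ongoing at Start of Study' = Yes. If an AE began between rollover consent and the first rollover dose, show it as other non-emergent so that the parts add up. The wider selection should not pull in parent-study stops, because exclusion criterion 1 in Protocol 5.3 bars patients permanently discontinued there.

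2. Use one anchor date in the SAP 15.1 definition, its worked example and the Appendix 2 note on AEs. The first rollover dose is consistent with the 15.1 definition and Protocol 9.6.1. If the appendix is moved to that date, its known-date rows also need the worsening clause from 15.1. At present they decide on start date alone and would turn worsened carried-over AEs into non-TEAEs.

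Item 1 gives the right count under either anchor, so it does not have to wait for item 2.

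Cost: SAP wording, one changed selection condition and a split in one output. The eCRF already collects both variables. The downside is that the AE-discontinuation figure may be slightly less favourable.
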